3.7. Exclusion Criteria

- subjects who have had surgery in the investigated area or lower extremity.
- subjects who have previously undergone physiotherapy.
- subjects with autoimmune diseases;
- subjects with peripheral neuropathy;
- subjects with calcific tendinopathy
- subjects with pain of direct traumatic origin;
- subjects with local/systemic infections;
- subjects with neoplastic diseases;
- subjects with gout;
- subjects on corticosteroid treatment at the time of enrollment;
- subjects who have used corticosteroids or fluoroquinolones in the three months prior to enrollment;
- subjects who have used NSAIDs in the week prior to enrollment.
- subjects who are pregnant and lactating;
- subjects with contraindications to acetaminophen use.
- allergy to porcine collagen.

3.8. Randomization and codification of subjects

Recruited subjects will be placed in Group A or B according to a 1:1 randomization list with 10 blocks of 9 subjects generated by software (2 blocks for each experimental center); the use of blocks will result in balanced groups.

A randomization list is planned for each Experimental Center comprising 18 subjects; the inclusion of subjects within the two experimental groups will take place progressively following the order of enrollment. Competitive enrollment is established among the participating Experimental Centers, which will end when the 72 subjects under the Clinical Investigation Plan have been enrolled. Each Experimental Center will be allowed to enroll a maximum of 18 subjects.

The randomization list will be kept by each Principal Investigator and the Clinical Research Unit of Guna S.p.a.

At the time of enrollment, each subject will be assigned a complex alphanumeric identification code consisting of the progressive enrollment number followed by an alphanumeric code generated through *Random Sequence Generator* at www.random.org.

The complex code is found to be in compliance with the current Privacy Regulations regarding coding of subjects participating in clinical trials.

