3.9.2 Visiting Plan

T0 BASAL: Enrollment

During the daily clinical activity, the investigators participating in the study will select subjects with achilles tendinopathy through the criteria given in section 3.16 and identify those meeting the inclusion and exclusion criteria. After fully explaining the purposes, aims and procedures in the study investigation plan, the subject will be offered participation in the study. Finally, the selected subject will be asked to view the information form and date and sign the Informed Consent

The subject according to the randomization list will be assigned to Group A or Group B.

We will then proceed with the objective examination and collection of the information required by the appropriately prepared Electronic Data Collection Form.

It will be followed by:

- assessment of VISA-A score
- assessment of pain according to the VAS scale
- administration of the SF-12 quality of life test.

Previous or ongoing drug treatments of any kind will be documented.

In order to monitor the consumption of analgesic used during the clinical investigation in case of pain onset (paracetamol 1000 mg), a clinical diary will be given to the subject in which to indicate the day and dose of medication used.

The enrolled subject will be given a complex alphanumeric identification code consisting of the progressive enrollment number followed by an alphanumeric code generated through Random Sequence Generator at www.random.org.

All enrolled subjects will be trained to practice physiotherapy for the 6 weeks in the clinical study plan. Subjects belonging to Group A will be administered MD-Tissue.

T1 week:

This visit will consist of an evaluation regarding the tolerability of the administered product. During this week, the subject will have received the first two infiltrations stipulated in the clinical investigation plan. It will be verified that the clinical diary regarding analgesic consumption used has been properly completed and that the physiotherapy course is proceeding according to the clinical investigation plan.

T2 weeks:

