### 3.8. Randomization and codification of subjects

Recruited subjects will be placed in Group A or B according to a 1:1 randomization list with 10 blocks of 9 subjects generated by software (2 blocks for each experimental center); the use of blocks will result in balanced groups.

A randomization list is planned for each Experimental Center comprising 18 subjects; the inclusion of subjects within the two experimental groups will take place progressively following the order of enrollment. Competitive enrollment is established among the participating Experimental Centers, which will end when the 72 subjects under the Clinical Investigation Plan have been enrolled. Each Experimental Center will be allowed to enroll a maximum of 18 subjects.

The randomization list will be kept by each Principal Investigator and the Clinical Research Unit of Guna S.p.a.

At the time of enrollment, each subject will be assigned a complex alphanumeric identification code consisting of the progressive enrollment number followed by an alphanumeric code generated through *Random Sequence Generator* at [www.random.org](http://www.random.org).

The complex code is found to be in compliance with the current Privacy Regulations regarding coding of subjects participating in clinical trials.

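### The fixed, printed blocks of 9 let staff partly predict later assignments by counting, so moving the list away from the Principal Investigators would not by itself secure concealment

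*Protocol*

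**What the plan says.** Section 3.8 is the same in both documents. It specifies a "1:1 randomization list with 10 blocks of 9 subjects generated by software (2 blocks for each experimental center"). It adds: "A randomization list is planned for each Experimental Center comprising 18 subjects". On the order of use it says that "the inclusion of subjects within the two experimental groups will take place progressively following the order of enrollment". Enrolment is competitive up to 72 subjects, and "Each Experimental Center will be allowed to enroll a maximum of 18 subjects". On custody it says: "The randomization list will be kept by each Principal Investigator and the Clinical Research Unit of Guna S.p.a".

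Section 3.9.2 gives recruitment to the sites: "the investigators participating in the study will select subjects with achilles tendinopathy". Section 3.11 gives Group A six injections and Group B physiotherapy only.

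Neither document describes a sham, masking, central release, sealed envelopes or varying block sizes.

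**The concern.** Block length, blocks per centre, list length and ratio all stand in the protocol that investigators work from. The arms differ visibly, so a site can tally its own past assignments. Towards the end of a block the tally points to the next arm, and sometimes fixes it. Someone who can guess the next arm can invite, delay or decline a patient accordingly.

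This adds to the custody problem. A Principal Investigator who holds the list has no need to count. But if the sponsor only moved the list off site, counting would still work, and changing 9 to another fixed number would not stop it.

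The primary endpoint is a questionnaire score (VISA-A at T8w) in patients who can tell their arm. Section 4.15 names ANCOVA without naming the covariate. If the covariate is the T0 VISA-A, adjustment removes only the selection that works through that score. Prognosis judged from activity level, motivation or symptom duration would stay in the treatment effect.

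**Working it through.** **Inputs from the documents.** Ten blocks of 9, two per centre, 18 places per list, cap of 18 per centre (3.8); N = 72 (3.5); difference 12, SD 15, R² 0.2, 28 analysed per arm, alpha 0.05 (4.14).

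**Assumptions.** The list is hidden from staff, who know the block length and their own centre's past assignments. Since 9 is odd, each block is taken as 5:4 or 4:5. Main case: the two blocks at a centre are complementary, giving 9:9. Alternative: the two splits are independent.

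**1. The plan's own power.** Residual SD = 15 × √(1 − 0.2) = 13.42. Noncentrality = 144 / (180 × 2/28) = 11.2. With 1 and 53 df the power is 90.75%, as stated. This point does not affect it.

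**2. Layout.** 10 / 2 = 5 centres and 5 × 18 = 90 places for 72 subjects. An even fill is 15/15/14/14/14. The other extreme is 72 / 18 = 4 full centres.

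**3. Predictability.** In a block with k places for A, after m places of which a went to A, P(next is A) = (k − a) / (9 − m). Where k is unknown, this is averaged over its posterior. The best guess is the larger of P and 1 − P. Enumeration for complementary blocks gives:

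| Places | Chance that the best guess is right | Sum |
|---|---|---|
| 1-9 | 0.500, 0.556, 0.556, 0.595, 0.595, 0.643, 0.643, 0.722, 0.722 | 5.532 |
| 10-18 | 0.556, 0.556, 0.595, 0.595, 0.643, 0.643, 0.722, 0.722, 1.000 | 6.032 |

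The chance that a place is known with certainty is 0.008, 0.048, 0.167 and 0.444 at places 6-9 (sum 0.667), and 0.008, 0.048, 0.167, 0.444 and 1 at places 14-18 (sum 1.667).

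- Five centres, accuracy: a 14-place centre gives 5.532 + 2.945 = 8.477 and a 15-place centre 9.120. Then (2 × 9.120 + 3 × 8.477) / 72 = 43.67 / 72, about 61%.
- Five centres, certain: 5 × 0.667 + 3 × 0.008 + 2 × 0.056 = 3.5 of 72.
- Four full centres: accuracy 11.56 / 18 = 64.2%; certain 4 × 2.333 = 9.3 of 72.
- Independent splits: 59.7% and 3.4 of 72 (five centres); 61.5% and about 5 of 72 (four full centres).

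**4. Effect on the primary comparison.** Suppose that staff shift the expected T8 score by +e when they expect A and by −e when they expect B. With guess accuracy q, bias ≈ 2e(2q − 1). The type I errors below are simulated with no true effect, residual SD 13.42 and about 28 analysed per arm.

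| Layout | Bias | e = 3 | e = 5 |
|---|---|---|---|
| Five centres | 2(2 × 0.606 − 1)e ≈ 0.4e | 1.3 points, about 6% | 2.1 points, about 8-9% |
| Four full centres, complementary | 2(2 × 0.642 − 1)e = 0.57e | 1.7 points, about 7.5% | 2.8 points, about 11% |

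**5. Alternatives.**

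| Scheme | Best-guess accuracy | Certain, of 72 | Bias |
|---|---|---|---|
| Present blocks, five centres | 60-61% | about 3.5 | about 0.4e |
| Present blocks, four full centres | 62-64% | about 5-9 | up to 0.57e |
| Big stick, limit 4 | about 54% | 5.5-6 (if the limit is known) | about 0.2e |
| Varied blocks of 4, 6 and 8 | 67% | about 2 | above the present blocks |

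In a four-centre simulation with a steering effect of 4 points, varied small blocks gave a bias of about 2.9 points and type I error of about 14%, against about 2.4 points and 11% for the present blocks.

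**The case against.** The strongest reply is that the scenario is hypothetical. Section 3.8 gives the list to each Principal Investigator, so nobody there needs to infer anything, and a new algorithm alone would leave that person with complete knowledge. This stands. Predictability is the secondary defect, and any remedy must deal with custody first.

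Three further replies stand in part.

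- A reader might infer that staff can generally know the next assignment. They cannot. Certainty covers about 5% of places in the five-centre layout and about 13% at four full centres with complementary blocks. Elsewhere it is a modest edge over chance. The always-known 18th place matters only at a centre that fills its list, and none does at 15/15/14/14/14.
- The size depends on e, which no document supplies, and on staff acting on every guess. Even at e = 5 with four full centres, the bias is 2.8 points against a 12-point target.
- Blocking by centre is a standard method, and the plan gives balance as its reason. An imbalance limit gives up some of that balance.

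These replies limit the size. They do not remove the mechanism: printed block length, visible assignments and recruitment by the same investigators are all in the plan, with no stated safeguard.

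**Conclusion.** The concern holds as a weakness that adds to the custody of the list. With the list hidden, the present scheme would still allow 60-61% correct guessing with five centres and 62-64% with four full ones, against 50% for an unpredictable list. The possible bias is about 0.4e in the implied layout and at most about 0.6e; type I error is about 6% to 9% with five centres and up to about 11% with four full ones, for e between 3 and 5.

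These figures rest on an undefined split of an odd block, on an assumed e, and on steering at every enrolment where the tally favours one arm. That past assignments are visible is inferred from the arms; neither document calls the trial open-label. A reader might also conclude that selection bias will occur, or that the block length is the main concealment failure. The documents support neither: they show an opportunity for steering, and the custody of the list is the larger failure. Sample size and power are not in question.

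**What to change.** Amend section 3.8 in two steps; both are needed.

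1. **Custody and release.** Remove the list from the Principal Investigators. Release each assignment centrally, one at a time, only after the patient is irrevocably enrolled, for example through the existing electronic data collection system or the sponsor's research unit. The allocation step in 3.9.2 should be reworded to match.
2. **Algorithm.** Replace the blocks of 9 with an imbalance-limit rule per centre. One example is big stick with limit 4: allocate 50:50 unless the centre's arm difference has reached 4, then allocate the lagging arm. Keep the limit in a restricted randomisation document.

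Together these give about 54% accuracy, bias of about 0.2e (0.6 points at e = 3) and type I error of about 5%.

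Costs to state: the mean overall arm difference is about 4 subjects (95% within 10). Power is 90.6% at 26:30 or 90.2% at 24:32, instead of 90.75% at 28:28. About 5.5-6 of 72 assignments are certain to anyone who learns the limit, which is more than the 3.5 under the present blocks with five centres, so the limit must stay confidential. No extra patients are needed and the lists must be regenerated. The documents do not say whether the data system can release assignments, so that set-up cost cannot be priced here.

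Varied block sizes of 4, 6 and 8 are not recommended: they reduce certain assignments but raise guess accuracy to 67% and raise the bias.

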3.11. Gruppi in studio

- **Group A (Collagen Medical Device):**

This Experimental Group will be treated with subcutaneous (s.c.) injections of 2 ml volume of:

- MD-Tissue (GUNA, Milan-Italy)

[figure not shown]
Composition for 2 ml: collagen 100 micrograms

Excipients: Ascorbic acid, Magnesium gluconate, Pyridoxine hydrochloride, Riboflavin, Thiamine hydrochloride, NaCl, Water for injection.

Subjects will be treated with No. 6 peri-tendon injections (2 infiltrations per week for three weeks).

- **Group B:**

This Experimental Group will implement only physiotherapy (eccentric strengthening protocol) for a period of 6 weeks.

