3.14. Criteria of effectiveness

3.14.1 Primary Endpoint

The primary end point will be assessed at T8s/FU and will involve:

- Assessment of the VISA-A questionnaire score at time T8w/FU compared to time T0. A difference between the two groups of 12 out of 100 points on the questionnaire can be considered clinically significant [17].

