4.15. Plan of statistical analysis

The primary endpoint will be evaluated by Ancova, as described in the numerosity calculation.

Secondary endpoints will be assessed as follows: 1) the VISA-A score at time T3s and T6s/FU compared with time T0 with Anova at repeated measures between group and within group; 2) the VAS at time T3s, T6s/FU and T8s/FU compared with time T0 with Anova at repeated measures between group and within group; 3) the SF12 questionnaire at time T3s, T6s/FU and T8s/FU compared with time T0 with Anova at repeated measures or Friedman's test; 4) the fraction of subjects in each group reaching Minimal Clinical Disease (MCD) considering that the MCD of the VISA-A questionnaire is 18.5 (90% MCD) with Fisher's exact test; 5) the units of analgesic drug consumed according to the clinical diary at time T3s, T6s/FUs and time T8s/FUs (paracetamol 1000 mg will be used as "rescue dose" in case of pain onset/recrudescence) with Friedman's exact test; 6) the fraction of subjects in each group who drop out of the investigation early in relation to Adverse Events (AE/SAE/SUSAR) with Fisher's exact test.

Statistical significance will be assumed for $p < 0.05$, unless corrected for multiple testing.

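### Each centre's Principal Investigator keeps the randomisation list, and nothing in the plan stops it being consulted before a patient is invited or entered

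*Protocol*

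**What the plan says.** Section 3.8 sets up one list per centre: "A randomization list is planned for each Experimental Center comprising 18 subjects". The list is worked through in sequence: "the inclusion of subjects within the two experimental groups will take place progressively following the order of enrollment". On custody it says: "The randomization list will be kept by each Principal Investigator and the Clinical Research Unit of Guna S.p.a". The same section prints the block size (9) and the number of blocks per centre (two). These statements are identical in the Protocol and in the combined protocol and SAP.

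Under T0 in section 3.9.2, recruitment is done at the centre: "the investigators participating in the study will select subjects with achilles tendinopathy". Identification of eligible patients, explanation and signed consent come first in the text. Then: "The subject according to the randomization list will be assigned to Group A or Group B". The T0 VISA-A, VAS and SF-12 assessments are listed after that sentence.

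Three other statements bear on the point. Group B receives no injection: "This Experimental Group will implement only physiotherapy (eccentric strengthening protocol) for a period of 6 weeks" (section 3.11). The primary endpoint is a questionnaire: "Assessment of the VISA-A questionnaire score at time T8w/FU compared to time T0" (section 3.14.1). The analysis is given as "The primary endpoint will be evaluated by Ancova, as described in the numerosity calculation" (section 4.15), and neither that section nor the sample-size section names the covariate.

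**The concern.** Randomisation protects against selection bias only if the next assignment is unknown while a patient is being considered, invited and judged eligible. Here the next free line of the centre's list is the next patient's arm, and the list is held where patients are recruited. Someone who knows that line can, deliberately or not, delay an invitation, press it harder, or read a borderline eligibility score one way or the other.

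Concealment before entry is a separate matter from blinding after entry, and it is fully achievable in an open trial. It matters more in this one. The arms are visibly different, no sham or blinding is described, and the outcome is self-reported, so few other protections remain. Adjustment is not a reliable repair. If the covariate is baseline VISA-A, the ANCOVA would not remove selection on other factors, such as how likely a patient is to keep up home exercises twice a day.

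**Working it through.** **Text check.** The question is whether anything in either document separates knowledge of the list from recruitment.

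- Holder: each Principal Investigator and the sponsor's Clinical Research Unit (section 3.8).
- Structure and use: a fixed list of 18 per centre, taken in order of enrolment (section 3.8).
- Recruiters: the participating investigators (section 3.9.2).
- Sequence: eligibility and consent are placed before assignment (section 3.9.2). This does not prevent reading the next line earlier.
- Random alphanumeric code: it identifies the subject for privacy (section 3.8) and does not conceal the arm.
- Central, telephone or web release, sealed envelopes, independent holder, restricted access, entry lock: none found in either document.
- Annexes: none of the titles listed in section 8 names a randomisation procedure.

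A person with the list knows 18 of 18 assignments. For comparison, take someone without the list who knows the printed block size and has seen past assignments. Suppose each block of 9 splits 5:4 in a known direction (an assumption; the documents do not give the split). Always guessing the arm with more places left is then right about 67% of the time, and about 1.7 of every 9 assignments are certain.

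**Reproducing the plan's power.** Inputs from the sample-size section: 28 per arm, difference 12, SD 15, R² 0.2, F-test at 0.05.

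- Residual SD = 15 × √(1 − 0.2) = 13.42.
- SE of the A − B difference = 13.42 × √(2/28) = 3.586; error df = 2 × 28 − 3 = 53.
- Noncentrality = (12/3.586)² = 11.2, which gives power 0.9075. The stated 90.75% is reproduced.
- If all 36 per arm complete: SE = 13.42 × √(2/36) = 3.162, with 69 df.

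**Illustration of what a bias would do.** Let b be a spurious difference between arms that remains after adjustment when there is no true effect. The rejection rate is that of the two-sided 0.05 test (equivalently the F-test) with noncentrality (b/SE)². Every value of b is assumed.

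| b (VISA-A points) | False-positive rate, 28 per arm | False-positive rate, 36 per arm |
|---|---|---|
| 0 | 5.0% | 5.0% |
| 0.5 | 5.2% | 5.3% |
| 1 | 5.9% | 6.1% |
| 2 | 8.5% | 9.6% |
| 3 | 13.0% | 15.5% |
| 5 | 27.8% | 34.4% |

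The rate reaches 10% at b = 2.38 points with 28 per arm (2.38/12 = 19.9% of the 12-point target) and at b = 2.09 points with 36 per arm (2.09/12 = 17.4%). A larger sample shrinks the SE but not the bias, so the rate rises.

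**The case against.** The text says only that the list is kept. The English reads as a translation, and the word could mean filed or archived. The plan does not say that the list is open, or that the Principal Investigator personally enrols patients. The flow chart (Fig. 1, Annex I) and the synopsis (Annex A) were not available to check. Section 3.9.2 already puts eligibility and consent before assignment, which is part of what a concealed procedure needs. The bias sizes are assumed, and at half a point or one point the effect is slight. Finally, withdrawing the list leaves some predictability while the block size is printed in the protocol and treatment is visible.

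Most of this is fair as a limit on certainty. It means that foreknowledge is permitted, not demonstrated, and that the figures show sensitivity rather than likelihood. It does not answer the point itself: the one custody rule that is written places the list at the recruiting site, and no safeguard accompanies it. The remark about block size stands and is taken into the fix. So does the caution that releasing assignments one at a time needs someone available whenever a centre enrols.

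**Conclusion.** The concern holds and should be corrected before enrolment. Confidence is high that the plan, as written, allows a recruiting site to know the next arm and describes nothing to prevent it. That conclusion rests on the custody rule alone. It assumes that each Principal Investigator holds at least his or her own centre's list, which is the natural reading of two adjacent sentences in section 3.8; if each holds every list, the problem is larger.

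The size of any resulting bias cannot be derived from the documents. A residual bias of about 2.1 to 2.4 points would double the false-positive rate; below one point the effect is small. Even if every site behaved properly, an outside reader could not rule out selection, and no analysis could reliably remove it afterwards.

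A secondary matter of wording does not affect this conclusion. Section 3.9.2 lists the T0 scores after assignment, although a VISA-A of 50 to 75 and a VAS of at least 5 are entry criteria and must be known beforehand. The text does not say whether the eligibility VISA-A is also the T0 value.

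**What to change.** In section 3.8:

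- Withdraw the list from the Principal Investigators. Leave it with the Clinical Research Unit, which already has it, or with another holder not involved in recruitment.
- State that each assignment is released only after consent, confirmed eligibility and irrevocable entry of the subject.
- Name the route. Telephone or email from the holder would do, since section 5.3 already uses both between the Principal Investigator and that unit for adverse events. So would the e-CRF, if it can do this, or sequentially numbered, sealed, opaque envelopes prepared outside the site. If envelopes must be on site, the centre pharmacy, which already receives the device (section 3.10), could hold them.
- Move the block size and the number of blocks per centre out of the protocol into a document that sites do not see.

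In section 3.9.2, state that the T0 scores are recorded before the assignment is released, and whether the eligibility VISA-A is the T0 value.

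The cost is protocol wording plus a small set-up task: preparing envelopes, or having someone available to release assignments. The documents describe the e-CRF only for data entry and adverse event reporting, so an allocation function in it should not be assumed. Patients may wait at T0 while the assignment is released; envelopes largely avoid this. Sample size, power and visits do not change.
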